8.1.3 Discontinuation Due to Further Progression (Confirmed Progression)

Participants will continue to receive monitoring according to the on-treatment assessments in Section 2. Radiographic assessment by CT (preferred) or MRI (described in Section 9.1) is required when participants continue post-progression study treatment and should be performed at each scheduled tumor assessment 4 to 6 weeks following initial disease progression to determine whether there has been continued progressive disease or not. Participants should discontinue study treatment upon evidence of further progression, defined as an additional 10% or greater increase in tumor burden volume from the time of initial progression (including all target lesions and new measurable lesions).

The tumor burden volume from the time of initial progression should be used as the reference baseline for comparison with the post-progression assessment.

Any new lesion considered non-measurable at the time of initial progression may become measurable and therefore must be included in the tumor burden measurement as follows:

• For solid tumors: new lesions are considered measurable at the time of initial progression if the longest diameter is at least 10 mm (except for pathological lymph nodes, which must have a short axis of at least 15 mm).

For statistical analyses that include the investigator-assessed progression date, participants who continue treatment beyond initial investigator-assessed, RECIST v1.1 or PCWG3 (prostate cancer only) defined progression will be considered to have investigator-assessed progressive disease at the time of the initial progression event.

For participants who discontinue post-progression study treatment, no additional radiographic assessments will be required.

8.1.4 Post-study Treatment Study Follow-up

Post-study follow-up is of critical importance and is essential to preserving participant safety and the integrity of the study. Participants who discontinue study treatment must continue to be followed up for the collection of outcome and/or survival follow-up data as required and in line with Section 5 until death or the conclusion of the study.

BMS may request that survival data be collected on all treated/randomized participants outside of the -defined window (Section 2). At the time of this request, each participant will be contacted to determine his or her survival status unless the participant has withdrawn consent for all contacts or is lost to follow-up.

Participants who discontinue study treatment may continue to be followed up.

8.2 Discontinuation from the Study

Participants who request to discontinue study treatment will remain in the study and must continue to be followed up for protocol-specified follow-up procedures, as indicated in Section 5.1.3. The only exception to this is when participants specifically withdraw consent for any further contact with them or persons previously authorized by participants to provide this information.

- Participants should notify the investigator of the decision to withdraw consent from future follow-up **in writing**, whenever possible.
- The investigator should explain the withdrawal of consent in detail in the medical records and enter on the appropriate CSR page as to whether the withdrawal is from further treatment with study treatment only or also from study procedures and/or post-treatment study follow-up; this explanation should be entered on the appropriate CRF page.
- In the event that vital status (whether the participant is alive or dead) is being measured, publicly available information should be used to determine vital status only as appropriately directed in accordance with local law.
- If the participant withdraws consent for disclosure of future information, the Sponsor may retain and continue to use any data collected before such a withdrawal of consent.

8.3 Lost to Follow-up

Guidelines for participants lost to follow-up include the following:

• All reasonable efforts must be made to locate participants to determine and report their ongoing status. This includes follow-up with persons authorized by the participant for contact.

- Lost to follow-up is defined by the inability to reach the participant after a minimum of **3** documented phone calls, faxes, or emails as well as lack of response by participant to **1** registered mail letter. All attempts should be documented in the participant's medical records.
- If it is determined that the participant has died, the site will use permissible local methods to obtain date and cause of death.
- If investigator's use of third-party representative to assist in the follow-up portion of the study has been included in the participant's informed consent, then the investigator may use a -retained third-party representative to assist site staff with obtaining the participant's contact information or other public vital status data necessary to complete the follow-up portion of the study.
- The site staff and representative will consult publicly available sources, such as public health registries and databases, to obtain updated contact information.
- If after all attempts the participant remains lost to follow-up, then the last known alive date, as determined by the investigator, should be reported and documented in the participant's medical records.

9 STUDY ASSESSMENTS AND PROCEDURES

- Study procedures and timing are summarized in the Schedule of Activities (Section 2).
- Protocol waivers or exemptions are not allowed.
- All immediate safety concerns must be discussed with the Sponsor immediately upon occurrence or awareness to determine if the participant should continue or discontinue treatment.
- Adherence to the study design requirements, including those specified in the Schedule of Activities (Section 2), is essential and required for study conduct.
- All screening evaluations must be completed and reviewed to confirm that potential participants meet all eligibility criteria before randomization. The investigator will maintain a screening log to record details of all participants screened and to confirm eligibility or record reasons for screening failure, as applicable.
- Procedures conducted as part of the participant's routine clinical management (eg, blood count) and obtained before signing of informed consent may be utilized for screening or baseline purposes provided the procedure meets the protocol-defined criteria and has been performed within the timeframe defined in the Schedule of Activities (Section 2).

Additional measures, including non-study-required laboratory tests, should be performed as clinically indicated or to comply with local regulations. Laboratory toxicities (eg, suspected drug-induced liver enzyme evaluations) will be monitored during the follow-up phase via on-site/local laboratories until all study treatment-related toxicities resolve, return to baseline, or are deemed irreversible.

If a participant shows pulmonary-related signs (hypoxia or fever) or symptoms (eg, dyspnea, cough, or fever) consistent with possible pulmonary AEs, the participant should be immediately

evaluated to rule out pulmonary toxicity according to the suspected pulmonary toxicity management algorithm in the ipilimumab IB.¹⁸

Some of the assessments referred to in this section may not be captured as data in the CRF. They are intended to be used as safety monitoring by the treating physician. Additional testing or assessments may be performed as clinically necessary or where required by institutional or local regulations.

9.1 Efficacy Assessments

Study evaluations will take place in accordance with the Schedule of Activities in Section 2.

Only data for the procedures and assessments specified in this protocol should be submitted to the Sponsor or designee on a CRF. Additional procedures and assessments may be performed as part of standard of care. However, data for these assessments should remain in the participant's medical record and should not be provided to the Sponsor or Designee, unless specifically requested from BMS or designee.

9.1.1 Methods of Assessment

CT and MRI are essential parts of the work-up to establish recurrence. The following imaging assessments should be performed at prespecified intervals: CT of the chest and CT or MRI of the abdomen, pelvis, and other known/suspected sites of disease.

- CT scans should be acquired with a slice thickness of 5 mm or less with no intervening gap (continuous).
- Should a participant have a contraindication for CT IV contrast, a non-contrast CT of the chest and a contrast-enhanced MRI of the abdomen and pelvis and other known/suspected sites of disease may be obtained. MRIs should be acquired with a slice thickness of 5 mm or less with no gap (continuous).
- Every attempt should be made to image each participant using an identical acquisition protocol on the same scanner for all imaging time points.
- PET alone will not be considered for the disease assessment. Complementary CT and/or MRI or biopsy must be performed in such cases.
 - Note: Use of CT component of a PET/CT scanner: Combined modality scanning, such as with fluorodeoxyglucose (FDG)-PET/CT, is increasingly used in clinical care and is a modality/technology that is in rapid evolution; therefore, the recommendations outlined here may change rather quickly with time. At present, low-dose or attenuation corrections of the CT portions of a combined FDG-PET/CT are of limited use in anatomically based efficacy assessments, and it is, therefore, suggested that they should not be substituted for dedicated diagnostic contrast enhanced CT scans for anatomically based RECIST v1.1 (see Appendix 5) or PCWG3 (prostate cancer only) (see Appendix 11) measurements. However, if a site can document that the CT performed as part of an FDG-PET/CT is of identical diagnostic quality to a diagnostic CT (with IV and oral contrast), then the CT portion of the FDG-PET/CT can be used for RECIST v1.1 measurements. Note, however, that the FDG-PET portion of the CT introduces additional data that may bias an investigator if it is not routinely or serially performed.

• Histology or cytological evidence of recurrence should be attempted in all cases except for brain metastases. Cytology and/or histology are mandatory to confirm recurrence in solitary or in equivocal lesions, any new lesions occurring in the kidney, and lymph nodes unless the lesion is too small to biopsy or the risk of biopsy is substantial (eg, inter-aortal node with risk of bleed after biopsy because of close proximity to the aorta and inferior vena cava), in which case, the recurrence must be confirmed with a repeat scan 4 weeks later.

Disease assessment with CT and/or MRI, as appropriate, will be performed at baseline and approximately Q8W (\pm 1 week) during the treatment phase (prior to dosing at Cycles 3, 5 and 7) until progressive disease per RECIST v1.1 (see Appendix 5) or PCWG3 (prostate cancer only) (see Appendix 11), or until confirmed progressive disease for participants treated beyond progression (defined as an additional 10% or greater increase in tumor burden volume from time of initial progression [including all target lesions and new measurable lesions]), or withdrawal from study. Tumor assessments at other time points may be performed if the investigator is concerned about tumor progression. Tumor response will be assessed by the investigator according to RECIST v1.1 (see Appendix 5) or PCWG3 (prostate cancer only) (see Appendix 11) for participants with solid tumors.

For participants with prostate cancer, bone lesions should be assessed using Technetium-99m (Tc-99m) based radionuclide bone scans. Anterior and posterior whole body planar images should be acquired. Additional (including spot views and SPECT) images should be submitted if acquired. Assessments should be performed at baseline and at the time points described per PCWG3 criteria until disease progression per PCWG3 criteria (see Appendix 11), or discontinuation of study treatment, whichever occurs later. Tumor assessments at other time points may be performed if clinically indicated and should be confirmed at least 4 weeks after initial response. Changes in tumor measurements and tumor responses will be assessed by the investigator per study design using PCWG3 criteria. Investigators will also report the number and size of new lesions that appear while on study. For participants who are treated beyond PCWG3-defined progression, tumor assessments will continue to be performed until discontinuation of study treatment (typically upon evidence of further progression). Any additional imaging that may demonstrate tumor response or progression (including scans performed at unscheduled time points and/or at an outside institution should be collected for PCWG3 tumor assessment and submitted to the BICR.

Images will be submitted to an imaging core laboratory. Sites should be trained prior to scanning the first study participant. Image acquisition guidelines and submission process will be outlined in the Imaging Manual to be provided by the core laboratory.

For Part A, images will be collected centrally and may be reviewed by BICR at a later date, or at any time during the study per BMS request. For Parts B, C, D and E, images will be collected centrally and reviewed by BICR.

9.1.2 *Primary Efficacy Assessments*

Not applicable.

9.1.3 Secondary Efficacy Assessments

The secondary efficacy assessments will include the objective response rate (ORR; eg, PR + CR), mDOR, and progression-free survival rate (PFSR) at 24 weeks based on assessment of tumor response using RECIST v1.1 or PCWG3 (prostate cancer only).

ORR is defined as the proportion of all treated participants whose best overall response (BOR) is either a CR or PR. BOR is defined as the best response designation over the study as a whole, recorded between the dates of first dose and the date of first objectively documented tumor progression per RECIST v1.1 (or PCWG3) or the date of subsequent therapy, whichever occurs first. CR or PR determinations included in the BOR assessment must be confirmed by a second scan performed no less than 4 weeks after the criteria for response are first met. A Best Overall Response of SD requires a minimum of 49 days on study from the date of first dose to the date of the first imaging assessment. For those participants who have surgical resection, only pre-surgical tumor assessments will be considered in the determination of BOR.

mDOR, computed for all treated participants with a BOR of CR or PR, is defined as the time between the date of first response and the date of the first objectively documented disease progression per RECIST v1.1 (or PCWG3) or death, whichever occurs first.

PFSR at 24 weeks is defined as the proportion of treated participants remaining progression free and surviving at 24 weeks. The proportion will be calculated by the Kaplan-Meier estimate, which takes into account censored data.

For prostate cancer, the consensus guidelines of the PCWG3 have been taken into consideration for the determination of radiographic disease progression assessment. All target and non-target sites of disease identified on the baseline assessment should be reassessed with the same imaging modality at subsequent assessments. Bone lesions should be assessed with Tc-99m based bone scans.

For prostate cancer disease progression, at each disease assessment, progressive disease will be determined using the criteria based on PCWG3.

Radiographic progression in soft tissue lesions (prostate only) is described in Table 9.1.3-1. See Appendix 11 (PCWG3) for additional information.

Parameter	Progression	Date of Progression
Soft tissue lesions (target, non- target lesions with CT or MRI)	Progression of soft tissue lesions (target, non-target, new lesions with CT or MRI)	Date of first unequivocal progression of soft tissue lesion (target, non-target, or new lesions) as per PCWG3 ^a
Bone lesions on radionuclide bone scan per PCWG3	At least 2 new lesions on the first post-treatment bone scan, confirmed on the next scan (performed at least 6 weeks later) AND with at least 2 additional lesions as compared to the first post-treatment bone scan	Date of first post-treatment scan
scan per r e wes	For scans after the first post- treatment scan, at least 2 new lesions relative to the first post- treatment scan AND confirmed on a subsequent scan (performed at least 6 weeks later)	Date of progression is the date of the scan that first documents at least 2 new lesions relative to the first post-treatment scan

Table 9.1.3-1:Definition of Radiographic Progression

^a RECIST v1.1 criteria are modified for assessing soft tissue lesions per PCWG3. See Appendix 11.

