Monitor for Non-serious AEs		Х								Non-serious AEs will be collected starting with the first dose of study treatment and through 100 days after last dose of study drug, or until new anti-cancer treatment is initiated, whichever comes first.
Monitor for SAEs					Х					See note in Table 2-1.

Procedures for Safety Cohort, and Parts A, B, C, D and E ^{a,b}				C2 to beyond	C2 Only	C2 Only		Notes		
Procedure	D1	D2	D8 ± 1 days	D15 ± 1 days	D22 ± 1 days	D1	D2	D8 ± 1 days	EOT c,d,e	
Sample Collection										
PK Assessments			See Ta	ble 9.5-1,	Table 9.5	9.5-4	See Section 9.5. To be performed in all participants.			
Immunogenicity Assessments			See Ta	ble 9.5-1,	Table 9.5	5-2, Table 9	9.5-4.			

Procedures for Safety Cohort, and Parts A, B, C, D and E ^{a,b}			C1			C2 to beyond	C2 Only	C2 Only		Notes	
Procedure	D1	D2	D8 ± 1 days	D15 ±1 days	D22 ± 1 days	D1	D2	D8 ±1 days	EOT c,d,e		
Efficacy Assessments											
Body Imaging						Every 8 weeks (± 1 week) prior to dosing at C3 and C5			X	See Section 9.1.	
Brain Imaging					per standa	y of brain n ard of care f illy indicate	See Section 9.1.				
Bone Scan					As clini	cally indica	ted.			See Table 2-1. See Section 9.1.	
Study Treatment Adminis	stration	Details regarding preparation and administration are provided in site training materials. In all study parts, participants will be observed for at least 60 minutes following the completion of BMS-986226 infusion due to the potential risk of, and to monitor for, infusion reactions.									

Procedures for Safety Cohort, and Parts A, B, C, D and E ^{a,b}			C1			C2 to beyond	C2 Only	C2 Only		Notes
Procedure	D1	D2	D8 ± 1 days	D15 ± 1 days	D22 ± 1 days	D1	D2	D8 ±1 days	EOT c,d,e	
All Parts: Premedication	Х					Х				In all study parts, participants are recommended to receive premedication 30 minutes prior to infusion of any study drug, to reduce the risk of infusion-related reactions, as described in Section 7.1 and Section 7.3.6. Any modification to the recommended regimen must be discussed and agreed upon with BMS Medical Monitor/Study Director.

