All Parts: BMS-986226 Administration	Х					Х				Use vials assigned per IRT. Safety Cohort and Part A BMS-986226 will be administered every 4 weeks on the first day of each cycle Parts B1 and C1: BMS-986226 will be administered on Day 1 every 12 weeks (Cycle 1 Day1, Cycle 4 Day1, Cycle 7 Day 1, etc) Parts B2 and C2: BMS-986226 will be administered every 4 weeks on the first day of each cycle Parts D and E: The dose and schedule of BMS-986226 will be determined based on available data from Parts A, B1, B2, C1 and C2.

Procedures for Safety Cohort, and Parts A, B, C, D and E ^{a,b}			C2 to beyond	C2 Only	C2 Only		Notes			
Procedure	D1	D2	D8 ± 1 days	D15 ±1 days	D22 ±1 days	D1	D2	D8 ±1 days	EOT c,d,e	
Parts B1, B2, and D ONLY: Nivolumab Administration	Х					Х				Use vials assigned per IRT. Nivolumab is administered ONLY for those participants enrolled in Parts B1, B2, and D.
Parts C1, C2, and E ONLY: Ipilimumab Administration	Х					X				Use vials assigned per IRT. Ipilimumab is administered ONLY for those participants enrolled in Parts C1, C2 and E.

^a The procedural outline for participants who receive additional cycles are outlined in Table 2-4.

^b Participants taking 2 or 8 mg of BMS-986226 in the Preliminary Safety Cohorts will follow the same procedure schedule as in Part A. In the event that participants taking 2 or 8 mg of BMS-986226 should be permitted to intra-dose escalate up to 8 and/or 25 mg, the sampling schedule should be restarted at Cycle 1 Day 1 at each dose escalation, and an additional tumor biopsy may be optionally re-collected at C1D15.

^c EOT is defined as the visit where a decision is made to discontinue the participant from treatment.

^d For participants who complete all scheduled cycles of therapy, the EOT visit will be the same as the last scheduled and completed on-treatment visit (eg, Cycle 6 Day 175) and the start of the Week 1 safety follow-up visit.

^e For participants who do not complete all scheduled cycles of therapy, the EOT visit will be the most recent on-treatment visit (with all available safety and response data) and does not need to be repeated, and it will be considered the start of the Week 1 safety follow-up visit.

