10.3 Statistical Analyses

The statistical analysis plan will be developed and finalized before database lock. Below is a summary of planned statistical analyses of the primary and secondary endpoints. In general, summaries will be performed by cohort. If sufficient data are not available such that adequate interpretation of the result is not warranted, some summaries may not be performed and only listings will be presented. Efficacy analyses will be performed using the RECIST v1.1 (all indications except prostate) or PCWG3 criteria (prostate). Details on censoring scheme on time-to-event endpoints such as DOR, PFS, and OS will be described in the SAP. A description of the participant population will be included in the statistical output reported, including subgroup of age, gender, and race.

Endpoint	Statistical Analysis Methods
ORR is defined as the proportion of all treated participants whose BOR is either CR or PR.	Estimate of ORR and corresponding 2-sided exact 95% CI using the Clopper-Pearson method
BOR for a participant will be assessed per RECIST v1.1 or PCWG3 (for prostate cancer) by investigator	
mDOR DOR for a participant with a BOR of CR or PR is defined as the time between the date of first response and the date of the first objectively documented tumor progression per RECIST v1.1 / PCWG3 or death, whichever occurs first.	mDOR using the Kaplan-Meier method and corresponding two 2-sided 95% CI using Brookmeyer and Crowley methodology (using log-log transformation), if appropriate
PFSR at 24 weeks PFS for a participant is defined as the time from the first dosing date to the date of first objectively documented disease progression or death due to any cause, whichever occurs first.	Estimate by the Kaplan-Meier method and corresponding 95% CI will be derived based on Greenwood formula

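### The 24-week PFS rate is read at exactly 24 weeks with no scan window, so in Part A progression first seen at a Day 175 end-of-treatment scan counts as progression-free

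*Combined protocol and SAP*

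**What the plan says.** **Endpoint.** Section 9.1.3 states: "PFSR at 24 weeks is defined as the proportion of treated participants remaining progression free and surviving at 24 weeks". It continues: "The proportion will be calculated by the Kaplan-Meier estimate, which takes into account censored data". Section 10.3 defines PFS as the "time from the first dosing date to the date of first objectively documented disease progression or death due to any cause", and gives the method as "Estimate by the Kaplan-Meier method and corresponding 95% CI will be derived based on Greenwood formula". No window is attached to the 24-week landmark. Section 10.3 leaves the censoring scheme to a later SAP. It does not mention the landmark or scans done off the nominal date.

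**Imaging.**
- Table 4-1 sets tumor measurements every 8 weeks ± 1 week on treatment. Section 7.3.1 counts the schedule from first dose, whatever the dosing delay.
- The body imaging row of Table 2-2 says "prior to dosing at C3 and C5" and also marks end of treatment (EOT). Section 9.1.1 instead says "prior to dosing at Cycles 3, 5 and 7".
- Section 5.1.2 gives monotherapy up to six 28-day cycles and requires each tumor assessment to be finished before the next cycle's dose.
- Footnote d of Table 2-2 says of participants who complete all cycles that "the EOT visit will be the same as the last scheduled and completed on-treatment visit (eg, Cycle 6 Day 175"). Table 2-4 repeats the example.

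**The concern.** A Kaplan-Meier curve drops only on the dates that events carry. If a scan meant to inform the 24-week rate takes place after day 168, any progression it finds is dated after the landmark, and that participant is counted as progression-free at 24 weeks. This error can only raise the rate.

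In Part A the exemplified EOT visit is already past the landmark, and no Cycle 7 dose pulls the scan earlier. The 24-week rate is one of three secondary efficacy measures, alongside ORR and median duration of response. What is at stake is whether a monotherapy figure labelled as Week 24 describes Week 24 or Week 16.

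**Working it through.** **Plan's own figure.** None. The protocol gives no assumed 24-week PFS rate, event count or target precision, so there is nothing to reproduce.

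**Dates, with first dose on Day 1.**
- Landmark: 24 × 7 = 168 days after first dose (Day 169).
- Week-24 scan window: 168 ± 7 = 161 to 175 days after first dose (Days 162 to 176).
- Part A treatment: 6 × 28 = 168 days. Cycle 6 runs from Day 141 to Day 168, so Day 175 does not lie in Cycle 6.
- Day 175 is 174 days after first dose, which is 6 days past the landmark.
- Cycle 7 Day 1 is Day 169, exactly 168 days after first dose.

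**Assumptions not in the documents.** PFS is exponential, S(t) = 2^(−t/m), with median m of 8, 12, 16 or 24 weeks. Scans at Weeks 8 and 16 are uniform within ± 7 days, and there is no dropout. Progression is dated at the next scan. Either 0% or 20% of events are deaths, dated exactly. Each case was simulated with 400,000 participants.

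**Three placements of the Week-24 scan.**
- (a) Day 175 for everyone still progression-free. The curve at 168 days reflects only the Week-16 scan, so the rate is about 2^(−16/m).
- (b) Within the 7 days up to an on-time Cycle 7 Day 1, on average 164.5 days (23.5 weeks) after first dose. The rate is about 2^(−23.5/m).
- (c) Uniform over the full ± 7 days. Of 15 possible days, 7 fall after the landmark, so the rate is about (7/15) × 2^(−16/m) + (8/15) × 2^(−23.5/m).

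For m = 12 these formulas give (a) 39.7%, (b) 25.7% and (c) 0.467 × 39.7 + 0.533 × 25.7 = 32.2%, matching the simulation to within 0.1 point.

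| Rate read at 168 days, no deaths | m = 8 | m = 12 | m = 16 | m = 24 | Overstatement, points |
|---|---|---|---|---|---|
| True rate | 12.5% | 25.0% | 35.4% | 50.0% | – |
| (a) Day 175 | 25.0% | 39.6% | 49.9% | 63.1% | 12.5 to 14.6 |
| (b) Before on-time Cycle 7 dose | 13.1% | 25.7% | 36.1% | 50.8% | 0.6 to 0.8 |
| (c) Uniform ± 1 week | 18.6% | 32.2% | 42.6% | 56.5% | 6.1 to 7.2 |

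The share of progressions found at the Week-24 scan but dated after the landmark is 100% in (a), 0% in (b) and about 49 to 50% in (c). With 20% of events as deaths, the overstatement is 10.0 to 11.8 points in (a), about 0.5 point in (b) and 5.0 to 5.9 points in (c).

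**Mixtures.** The bias is linear in the share scanned late. If half of those still progression-free in Part A are scanned on Day 175 and half as in (b), then for m = 12 it is 0.5 × 14.6 + 0.5 × 0.7 = 7.7 points.

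**Scale.** At a 25% rate the binomial standard error is √(0.25 × 0.75/40) = 6.8 points for an expansion arm of 40, and √(0.25 × 0.75/12) = 12.5 points for a Part A dose level at its ceiling of 12.

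**Reading the curve at 175 days instead, no deaths.** Case (a) gives 11.5/23.7/34.1/48.8%, which is 1.0 to 1.3 points low. Case (c) gives 12.4/24.9/35.3/50.0%, essentially the true rate. Case (b) is unchanged at 13.1/25.7/36.1/50.8%.

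**The case against.** The case on the other side is strong on size and scope.

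- **Parts B to E.** Sections 5.1.2 and 9.1.1 place the Week-24 scan before the Cycle 7 dose. A participant dosed on time therefore has it no later than day 168. A reader might infer a general overstatement of 6 to 7 points from the ± 1 week window, but that needs scans spread evenly over the whole window, which the pre-dose rule does not produce. Late scans remain possible when dosing slips, and Table 2-2 does not name Cycle 7. A convention that counts the first dose as day 1 of PFS would also put a Day 169 scan at 169 days.
- **Part A.** Day 175 is only an example of a visit date and does not fit Cycle 6. The every-8-weeks rule allows a scan from Day 162. Under Section 5.1.4 some completers may receive a further 24 weeks, and their scan should then precede the next dose. A reader might take 12 to 15 points as the Part A error. It is the upper case, in which every participant still progression-free is scanned on Day 175.
- **Deaths and unscheduled scans.** Deaths are dated exactly, and Section 9.1.1 allows extra scans when progression is suspected. Both reduce the bias.
- **Consequence.** The Synopsis states that no hypotheses are formally evaluated, no threshold is set for this rate, and Section 10.3 summarizes by cohort. A reader might infer that a monotherapy-versus-combination comparison is compromised, but none is planned.

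All of this stands. Deferral to the SAP does not fully answer the point, because what Section 10.3 defers is the censoring scheme, not the landmark or how scans in the window are treated.

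**Conclusion.** The mechanism and its upward direction follow from the documents: a landmark without a window, events dated at the scan, and a scan window that straddles the landmark. The material case is Part A participants who stop at 24 weeks and are scanned at an EOT visit on or near Day 175. If all are scanned then, the reported rate is in effect the Week-16 rate, about 12 to 15 points too high, or 10 to 12 with 20% deaths. Those sizes rest on exponential PFS with medians of 8 to 24 weeks and on an example date. Earlier scans or additional cycles shrink them.

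In Parts B to E the bias is under 1 point with on-time dosing and approaches 6 to 7 points only if scans fill the window evenly. The documents give no PFS rate and no distribution of scan dates, so they do not support saying that many Week-24 progressions are miscounted. For a descriptive endpoint without a decision threshold, this is a modest correction worth making.

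**What to change.** 1. In Sections 9.1.3 and 10.3, and in the SAP, read the 24-week PFS rate from the Kaplan-Meier curve at the end of the Week-24 assessment window (175 days after first dose, Day 176). Alternatively, for this estimate, assign progression found at the Week-24 (± 1 week) scan to the nominal Week-24 date. State whether the first dose counts as day 0 or day 1.
2. Reconcile the body imaging row of Table 2-2, its footnote d and Section 9.1.1 on when the Week-24 scan is done, including for Part A participants with no Cycle 7.

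The cost is a sentence or two of text and one table entry. No scans are added, because the every-8-weeks schedule already covers Week 24. The reported rate will be somewhat less favourable wherever scans fall after day 168, and with Day 175 scans the Week-25 reading runs about 1 point low. The residual of under 1 point from scanning before an on-time Cycle 7 dose stays, because it comes from looking slightly early.
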